9.1 Statistical Analysis

This is paired sample study of FNB vs FNA for whole exome sequencing and genomic profiling. For descriptive analyses, continuous variables will be reported as a mean \pm SD or median (interquartile range) and comparison between two groups will be done by Paired *t*- test. Categorical variables will be reported as frequencies with percentages and compared using chi-square test or Fisher’s exact test. Two sided P values less than 0.05 will be considered statistical

significance. Descriptive analysis will be performed in terms of DNA yield per sample, histology and cytology yield per sample. Sample size calculation is done after interim analysis. **Sample**

size calculation:

From our preliminary data from 5 PDAC patients and using the Foundation Medicine adequacy criteria, 2 (40%) had an adequate sample of DNA with FNA, while all 5 (100%) patients had adequate DNA with FNB. Although this is a very small sample size it is consistent with the notion that FNB may be much superior to FNA. Based on this preliminary data, it seems reasonable to expect that the difference in proportions of adequate samples by the two methods might be 25% or more. Assuming we have 50 patients who all are sampled with both FNA and FNA, then with a McNemar's test we will have 80% or higher power to detect a difference in adequacy proportions between FNA and FNB (at the 5% significance level) of $\geq 25\%$ if $\leq 38\%$ of patients have discordant results for FNA and FNB, or a difference of $\geq 20\%$ if $\leq 25\%$ are discordant. The following are just 3 of many possible examples of scenarios whereby we will have sufficient power with a sample size of 50 patients, all of which are consistent with the findings in the preliminary data:

Example A (25% difference):

		FNA adequate?		
		Yes	No	
FNB adequate?	Yes	$\geq 58.5\%$	$\leq 31.5\%$	90%
	No	$\leq 6.5\%$	$\geq 3.5\%$	10%
		65%	35%	

Example B (25% difference):

		FNA adequate?		
		Yes	No	
FNB adequate?	Yes	$\geq 48.5\%$	$\leq 31.5\%$	80%
	No	$\leq 6.5\%$	$\geq 13.5\%$	20%
		55%	45%	

Example C (20% difference):

		FNA adequate?		
		Yes	No	
FNB adequate?	Yes	$\geq 68\%$	$\leq 22\%$	90 %
	No	$\leq 2\%$	$\geq 8\%$	10 %
		70 %	30 %	

References:

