8.2 Study Protocol

- 1) Filling the “Pre-Procedure Patient Registration” section of the “Registration and Data Collection” form
- 2) Review of the signed informed consent before the start of procedure.
- 3) All patients will undergo conscious sedation or Monitored Anesthesia Care (MAC) for the duration of the procedure. Conscious section and/or MAC are the standard method of sedation for all patients that have EUS at our institution, unless contraindicated.
- 4) Morphologic features of the lesion will be examined and documented in the procedure report. Based on the location and type of the lesion, the participating endosonographer determines the necessity of performing an FNA. If FNA deemed necessary, the patient will be included in the study.

- 5) Randomization of needle order. The first needle to be used will be selected by randomization using block randomization in envelopes (FNA first, FNB first) by tumor location (1 block for head tumors, 1 block for body/tail tumors).
- 6) Conventional FNA will be alternated with FNB (22 gauge for all sites) in the usual fashion for obtaining histological material. A minimum of 2 passes (1 with each needle) will be obtained from all lesions. Conventional FNA will be performed with a standard 25g needle (our standard needle) in the usual fashion using back and forth passes for 30 seconds. Negative pressure will be applied for both needle types using the “capillary” technique of withdrawing the stylet slowly (5-10cm per second) during the to and fro movement of the needle. All FNA material will be expressed onto a glass slide. Visible core samples will be removed and placed in formalin after an initial “touch prep” (light touch of tissue to slide). The presence or absence and length (in mm) of grossly visible each core will be recorded by the cytotechnologist/study personnel. Standard passes (alternating with each needle) will be repeated in pairs until an adequate sample is obtained or the endoscopist feels that no further sampling is warranted. Then, a 2nd and 3rd set of passes (one with each needle) will be performed to collect material for biobanking and DNA and RNA extraction. The sample will be expressed into a sealed biospecimen container and flash frozen in liquid nitrogen, then stored at -80C. If no material is obtained, the research pass will be repeated up to a maximum of 2 passes for each needle.

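### Section 9.1 and the synopsis name unpaired tests (chi-square or Fisher's exact) for yes/no outcomes paired within patient, while the 80% power is stated for McNemar's test and is not assured with the named tests

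*Combined protocol and SAP*

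**What the plan says.** Section 9.1 opens with the design: "This is paired sample study of FNB vs FNA for whole exome sequencing and genomic profiling". Section 8.2 makes the pairing concrete: "A minimum of 2 passes (1 with each needle) will be obtained from all lesions"; randomization only decides which needle goes first.

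For continuous outcomes the plan respects the pairing: "comparison between two groups will be done by Paired" t-test. For yes/no outcomes it does not: "Categorical variables will be reported as frequencies with percentages and compared using chi-square test or" Fisher's exact test. The synopsis repeats this rule, and in both places the two-sided 0.05 criterion follows directly.

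The sample size paragraph of section 9.1 uses another test: "then with a McNemar's test we will have 80% or higher power to detect a difference in adequacy proportions between FNA and FNB". The conditions are a difference of at least 25 points with at most 38% discordant patients, or at least 20 points with at most 25% discordant. Three worked tables follow, introduced by: "The following are just 3 of many possible examples of scenarios whereby we will have sufficient power with a sample size of 50 patients". No section names McNemar's test, or any other paired test, as the analysis of adequacy.

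**The concern.** Chi-square and Fisher's exact test treat the 50 FNB results and the 50 FNA results as coming from 100 unrelated patients. Here they come from the same 50 lesions. The mismatch reaches the comparison that sizes the trial, and with it DNA sufficiency for whole exome sequencing, targeted profiling, cytology and histology.

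Two things are at stake. First, the stated power belongs to a test that the analysis text does not name. McNemar's power depends only on the difference and the discordance, which are the two quantities the plan specifies. The power of the unpaired tests also depends on the adequacy rates, on which the plan sets no condition. Second, with three candidate tests in the text and no rule for choosing, including none for when Fisher replaces chi-square, the conclusion could turn on a choice made after the data are seen.

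**Working it through.** **Inputs.** From section 9.1: n = 50 pairs; two-sided 5%; Examples A to C; the limits 25 points/38% and 20 points/25%; and the pilot FNA rate, "2 (40%) had an adequate sample of DNA with FNA". Write p10 for adequate with FNB only, p01 for adequate with FNA only, ψ = p10 + p01 for discordance and δ = p10 − p01 for the difference. Examples A and B: 31.5 + 6.5 = 38% and 31.5 − 6.5 = 25 points. Example C: 22 + 2 = 24% and 22 − 2 = 20 points.

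**1. The plan's own figure.** The number of discordant pairs is M ~ Bin(50, ψ). Given M = m, the FNB-only count is B ~ Bin(m, p10/ψ). Exact McNemar rejects when 2·P(Bin(m, ½) ≤ min(b, m − b)) ≤ 0.05. Summing over all m and b:
- 25 points: 81.2% at 38% discordant, 79.7% at 39%.
- 20 points: 80.8% at 25% discordant, 78.3% at 26%.

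The plan's limits are those of exact McNemar, and the power statement is correct for that test.

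**2. The named tests on the same paired data.** I enumerated every four-cell table with 50 pairs. With x and y the adequate counts for FNB and FNA, I applied uncorrected chi-square, z = (|x − y|/50)/√(2p̄(1 − p̄)/50) with p̄ = (x + y)/100, and Fisher's exact test to x of 50 against y of 50.

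| FNB vs FNA, discordant | Exact McNemar | Chi-square | Fisher |
|---|---|---|---|
| Example A: 90 vs 65%, 38% | 81.2% | 87.7% | 82.0% |
| Example B: 80 vs 55%, 38% | 81.2% | 80.2% | 73.1% |
| Example C: 90 vs 70%, 24% | 83.5% | 78.3% | 66.9% |
| 95 vs 75%, 25% | 80.8% | 86.9% | 76.3% |
| 90 vs 70%, 25% | 80.8% | 77.7% | 66.5% |
| 80 vs 60%, 25% | 80.8% | 62.7% | 51.4% |
| 60 vs 40%, 25% | 80.8% | 55.5% | 43.2% |
| 65 vs 40%, 38% | 81.2% | 77.5% | 69.3% |

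The rates below Example C are assumptions, except that 90 vs 70% takes Example C's rates and the 40% for FNA is the pilot rate. All of them meet the plan's stated conditions on difference and discordance. Uncorrected McNemar, the like-for-like comparison for uncorrected chi-square, gives 87.0%, 87.0% and 89.5% in A, B and C.

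**3. Why.** The difference in proportions has standard error √[(ψ − δ²)/n] in paired data. The unpaired tests in effect use √[(p1q1 + p2q2)/n], with p1 and p2 the two adequacy rates and q = 1 − p.
- Example A: √[(0.38 − 0.0625)/50] = 0.0797 and √[(0.09 + 0.2275)/50] = 0.0797. They are equal because the cells imply zero within-patient correlation, so nothing is lost.
- Example C: √[(0.24 − 0.04)/50] = 0.0632 against √[(0.09 + 0.21)/50] = 0.0775.
- 60 vs 40%, 25% discordant: √[(0.25 − 0.04)/50] = 0.0648 against √[(0.24 + 0.24)/50] = 0.0980.

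**4. Fewer discordant pairs.** At 60 vs 40%, going from 25% to 20% discordant lifts exact McNemar from 80.8% to 95%, but chi-square stays at 55.5–55.6% and Fisher at 42–43%. With p̄ = 0.5, chi-square needs a gap of 10 patients (z = 0.20/0.10 = 2.0), which is exactly the expected gap (0.20 × 50), so power stays near one half. At 65 vs 40%, chi-square reaches 80.8% once discordance is down to 30%; Fisher stays at or below 74%.

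**5. Patients needed.** At 60 vs 40% with 25% discordant, 80% power takes about 80 patients with chi-square and about 90 with Fisher (simulation in steps of 5).

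**6. Type I error.** With both needles at 80% adequate (assumed), chi-square rejects 2.9% of the time at 25% discordance and 7.4% at 38%. Independent results would give 2 × 0.8 × 0.2 = 32% discordant, so 38% implies negative correlation.

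**7. One data set, three answers.** Suppose 10 patients are adequate with FNB only and 1 with FNA only, with totals 34/50 and 25/50. Exact McNemar p = 0.012, chi-square p = 0.067, Fisher p = 0.103.

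**The case against.** The best defence is that the intended test is visible. McNemar's test stands inside section 9.1, attached to the adequacy comparison, while the chi-square/Fisher sentence sits under descriptive analyses; chi-square might even be loose wording for McNemar's chi-square. That shows likely intent but does not settle it. The significance rule follows the chi-square/Fisher sentence directly, that sentence pairs chi-square with an independent-samples test, and no other categorical analysis is specified.

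Second, the largest shortfalls come from 60 vs 40%, far from the pilot's 100% vs 40%. This is fair as to size. With FNA kept at 40%, chi-square and Fisher give 92.7% and 88.2% at 70% FNB (38% discordant), and 99.9% and 99.8% at 80% FNB (40% discordant). Chi-square is at worst 2.5 points short in the 25-point cases above, and it beats exact McNemar in Example A and at 95 vs 75%. But the plan claims power for any rates within its limits, and Fisher falls short in two of its own three examples.

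Third, McNemar reproduces the power only for 50 complete pairs, and the margin is thin: at 25 points and 38% discordant, 48 pairs give 79.3%. This stands as a limit on what the check shows. It does not favour the named tests.

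Fourth, McNemar does not suit safety, which section 2.2 plans as a historical comparison, and repeated passes require one result per needle. Both are matters of wording: the safety comparison is not paired, and the per-needle aims already imply one result per needle per patient.

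**Conclusion.** The concern holds. Followed literally, the plan applies independent-groups tests to matched pairs in the comparison that sizes the trial, and its power statement belongs to a different test. Not assured is the right strength: with chi-square the plan's examples give 78.3% to 87.7%, with Fisher 66.9% to 82.0%. Elsewhere within the stated limits, power falls as low as 55.5% and 43.2% in the cases tabulated. Those lowest figures rest on assumed rates of 60% vs 40% at the smaller 20-point difference; if the true difference is as large as the pilot suggests, any of the tests would detect it. With McNemar as the analysis test, the power arithmetic for 50 complete pairs stands as written.

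**What to change.** In section 9.1 and the synopsis:
- Name McNemar's test on patient-level pairs, one result per needle per patient, for the paired yes/no outcomes: DNA sufficient for whole exome sequencing, targeted profiling, cytology and histology.
- Pre-specify the version (exact, mid-p or uncorrected). The exact test is the one that reproduces the plan's 38% and 25% limits.
- Report the paired difference in proportions with a 95% confidence interval for paired data.
- Keep chi-square or Fisher's exact test for unpaired comparisons only, such as head versus body/tail tumors or the historical safety comparison, and state when Fisher is used.

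The cost is wording in two places. No new data are needed and the sample size stays at 50.

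### Section 9.1 powers the paired adequacy comparison on an unspecified McNemar test but names chi-square or Fisher tests for its analysis; pre-specifying mid-P McNemar would settle this and add 5 to 6 points of power at the planning limits.

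*Combined protocol and SAP*

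**What the plan says.** The sample size text in 9.1 (Combined protocol and SAP) starts from "Assuming we have 50 patients who all are sampled with both FNA and FNA", where the second needle is evidently meant to be FNB. It continues that, with a McNemar test, "we will have 80% or higher power to detect a difference in adequacy proportions between FNA and FNB", tested "at the 5% significance level". The claim holds for a 25-point difference "if $\leq 38\%$ of patients have discordant results for FNA and FNB", "or a difference of $\geq 20\%$ if $\leq 25\%$ are discordant". Three example tables follow.

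The analysis paragraph of 9.1 calls the study a paired-sample study and uses a paired t-test for continuous variables. For categorical variables it lists only the chi-square and Fisher tests. The synopsis repeats this. The decision rule is "Two sided P values less than 0.05 will be considered statistical" significance. No version of McNemar's test (exact, mid-P, uncorrected or continuity-corrected) is named anywhere.

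**The concern.** Two gaps meet in one comparison. First, the test that supports the power statement is missing from the analysis text, and the tests that are listed are normally used for independent groups. Each patient contributes one FNB and one FNA result, so a test that ignores the pairing has different power from the one promised.

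Second, the version of McNemar's test matters with 50 pairs. At 25% to 38% discordance, about 12 to 19 patients carry the information. With so few, the exact test can use only a coarse set of p-values and falls well short of its nominal 5% level. With the sample fixed at 50, power is then given up for no stated reason.

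**Working it through.** **Inputs.** From 9.1: N = 50 pairs, two-sided 5%, and two scenarios (difference 25 points with 38% discordant; 20 points with 25% discordant). Section 3.5 replaces patients who do not complete, so 50 complete pairs are assumed.

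**Cell probabilities.** With difference d and discordance D, the FNB-only cell is (D + d)/2 and the FNA-only cell is (D − d)/2.
- Scenario 1: (0.38 + 0.25)/2 = 0.315 and (0.38 − 0.25)/2 = 0.065, as in Examples A and B.
- Scenario 2: (0.25 + 0.20)/2 = 0.225 and (0.25 − 0.20)/2 = 0.025.
- Example C uses 0.22 and 0.02, which sum to 24% discordance.

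**Method.** Full enumeration. The number of discordant pairs n is Binomial(50, D). Given n, the FNB-favouring count is Binomial(n, FNB-only cell / D). Power sums the probability of all outcomes with p ≤ 0.05. True error is the same sum with the two discordant cells equal. With k the smaller discordant count and probabilities taken at one half:
- exact p = 2·P(X ≤ k);
- mid-P p = exact p − P(X = k).

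**Reproducing the plan's figure, and the alternatives.**

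| McNemar version | Power 25/38 | Power 20/25 | Power Ex. C | Error at 38% | Error at 25% | 80% limits on D |
|---|---|---|---|---|---|---|
| Exact | 81.2% | 80.8% | 83.5% | 3.0% | 2.5% | 38.8%, 25.3% |
| Continuity-corrected | 79.4% | 80.6% | 83.4% | 2.6% | 2.3% | 37.5%, 25.2% |
| Mid-P | 86.1% | 87.1% | 89.3% | 4.6% | 4.4% | 42.7%, 28.5% |
| Uncorrected chi-square | 87.0% | 87.2% | 89.5% | 5.2% | 4.4% | 44.6%, 28.5% |

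The exact limits round down to the plan's 38% and 25%, and only the exact version both meets 80% at each stated limit and sits close to it. The mid-P test matches the power of the exact test with 57 patients (25/38) or 58 (20/25).

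**Where the gain arises.** Take 14 discordant pairs split 11 to 3. Exact p = 2 × (1 + 14 + 91 + 364)/16384 = 940/16384 = 0.057, not significant. Mid-P p = 0.057 − 364/16384 = 0.035, significant. At 12, 13, 15, 17 and 18 discordant pairs the two tests reject the same outcomes. They differ at counts such as 11, 14, 16 and 19.

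**Error of mid-P.** At 50 pairs its unconditional error is at most 5.0% from 5% to 95% discordance. It passes 5% at 95.5% and reaches 6.5% at 100%. Conditional on the discordant count it can exceed 5%: 6.5% at 11, 5.7% at 14, 7.7% at 16 and 6.4% at 19.

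**The listed tests, run unpaired on the example tables (N = 50 per needle).**

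| Example | Chi-square | Fisher | Exact McNemar | Mid-P McNemar |
|---|---|---|---|---|
| A | 87.7% | 82.0% | 81.2% | 86.1% |
| B | 80.2% | 73.1% | 81.2% | 86.1% |
| C | 78.3% | 66.9% | 83.5% | 89.3% |

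Example A shows no loss because its table implies no correlation between needles: 0.90 × 0.65 = 0.585, exactly the both-adequate cell. In B and C the both-adequate cells exceed independence (0.485 against 0.80 × 0.55 = 0.440; 0.68 against 0.90 × 0.70 = 0.630), and ignoring the pairing costs power.

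**Away from the limits.** At 25 points with 30% discordance, power is 92.6% exact and 95.5% mid-P. At 30 points with 35% discordance it is 97.6% and 98.7%.

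**The case against.** The plan promises "we will have 80% or higher power" and the exact test delivers it, so no power figure is wrong. Sizing a trial on a test that guarantees its level is legitimate. This stands in full.

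A reader might infer that the trial will run the exact test and leave up to half of its 5% unused. The documents do not support that. The exact version is inferred from the 38% and 25% limits, and the continuity-corrected version fits nearly as well. The test used for sizing need not be the one run. If the uncorrected chi-square McNemar is run, power is already about 87% and the gain from mid-P vanishes, although its error is 5.2% at 38% discordance and 5.4% at 50%.

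A reader might also infer that the analysis will certainly ignore the pairing and lose power. That goes too far as well. McNemar's test is itself a chi-square test, the paragraph calls the study paired, and in Example A the unpaired chi-square loses nothing. What remains is that the text does not say which test will be used, and that the tests as listed fall below 80% in some of the plan's own examples.

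Finally, the 5 to 6 points apply at the planning limits and shrink for larger effects or lower discordance. The error control of mid-P holds on average over discordant counts, not at each count. Both limits stand and should be stated with the recommendation.

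**Conclusion.** The point holds as a cheap improvement, not as an error in the stated power. The substantive part is the missing paired test: 9.1 is powered on McNemar, while its analysis text, read as unpaired tests, gives 80% or 73% power in Example B and 78% or 67% in Example C. The choice of mid-P is a refinement of that correction. Against the exact test it raises power from 81.2% to 86.1% (25/38) and from 80.8% to 87.1% (20/25), with true error of 4.6% and 4.4%. This rests on 50 complete pairs, the plan's own discordance limits, and the inference that the exact version lies behind the sample size.

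**What to change.** In 9.1, and in the synopsis where the same text appears:
- For the paired FNB-versus-FNA adequacy comparison, replace chi-square/Fisher with a two-sided mid-P McNemar test at 5%, specified before the results are analysed, and give its definition.
- Restate power with 50 pairs as about 86% (25 points, 38% discordant) and 87% (20 points, 25% discordant), or as 80% with discordance limits of about 42% and 28%.
- Report the exact McNemar p-value as a sensitivity result.

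The cost is a sentence or two and no extra patients. The downside is that mid-P does not guarantee 5% by construction, and its error exceeds 5% at some discordant counts. The enumeration should be rerun if the final number of pairs is not 50.

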8.1 PATIENT REGISTRATION AND DOCUMENTATION

8.2 STUDY PROTOCOL

9. STATISTICAL CONSIDERATIONS

9.1 STATISTICAL ANALYSIS 26

Steering Committee

Principal Investigator: [name] [name]
Professor of Medicine
Division of Gastroenterology and Hepatology
Mayo Clinic
[contact]

Coinvestigators: [name]
Division of Gastroenterology and Hepatology
Mayo Clinic
[contact]

[name].
Division of Gastroenterology and Hepatology
Mayo Clinic
[contact]

[name].
Division of Gastroenterology and Hepatology
Mayo Clinic
[contact]

[name].
Research Fellow
Division of Gastroenterology and Hepatology
Mayo Clinic

[contact]

Biostatistician

[name] Ph.D.

Biostatistics Unit

Mayo Clinic

[contact]

Pathologist:

[name] M.D.

Department of Pathology

Mayo Clinic

[contact]

Protocol Synopsis

Title of Study	Endoscopic ultrasound guided core biopsy needle versus fine needle aspiration (FNA) needle in tissue sampling of pancreas cancer for whole exome sequencing and genomic profiling: a prospective randomized controlled trial.
Hypothesis	Flexible core biopsy needles are more capable than fine needle aspiration in acquisition of tumor tissue that is important for pathological evaluation and genomic analysis. This would specifically allow us to perform whole exome sequencing of a tumor tissue and could provide path for future individualized pancreas cancer treatment. Thus, we hypothesized that FNB is superior to FNA in acquiring tumor tissue from pancreas mass that is key for genomic profiling.
Specific Aims	To compare FNB versus conventional FNA for whole exome sequencing and genomic profiling in tissue sampling of pancreas cancer. 
1. Per needle adequacy for un-amplified whole exome sequencing2. Per needle quantity of DNA.3. Per needle adequacy for cytology4. Per needle adequacy for histology5. Adverse events
Study design	Prospective, single blinded, randomized controlled trial of FNB versus FNA for whole exome sequencing and genomic profiling.

Sample size	50cases
Inclusion criteria	
 ▪ Male and female patients who are 18 years old or older and are referred for the evaluation of pancreatic mass lesion ▪ International Normalized Ratio (INR) less than 1.5 and platelet count of more than 50,000. ▪ Medically stable to undergo sedation for EUS. ▪ Signed informed consent

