2. STUDY OBJECTIVES

2.1 Primary Objective:

To compare EUS guide fine needle biopsy versus fine needle aspiration for whole exome sequencing and genomic profiling in tissue sampling of pancreatic solid tumors.

2.2 Secondary Objectives:

- To compare the DNA yield of FNB versus FNA in tissue sampling of pancreas cancer including sufficient DNA to complete un-amplified whole exome sequencing.
- To compare the number of needle passes necessary to obtain adequate tissue sample to make a cytological/histological diagnosis when FNB is used as compared to the conventional FNA for pancreas cancer
- To compare the histology quality of the specimens obtained via FNB as compared to conventional FNA.
- To compare the yield of tissue sufficient for targeted (Foundation Medicine Assay) genomic profiling of pancreas tumors.
- To estimate the safety profile of FNB as compared to conventional FNA. (by historical comparison)
- Per needle adequacy for cytology

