13) DNA extraction and quantification: One or two biopsy tissues are first digested, then DNA extractions will be performed using the silica membrane-based column DNA extraction method with the QIAamp DNA Mini Kit. This column based extraction method provides purified DNA which is free of protein, nucleases and other contaminants or inhibitors. This kit is used for fresh or frozen tissue, cells, and blood. If larger tissue samples are obtained; the Puregene DNA extraction will be used and is a salt precipitation method. Tissues are lysed and DNA is precipitated from the cells. This method allows for purification of high molecular weight DNA for downstream use.

For DNA quantification, the Trinean DropSense96 spectrophotometer will be used which is a multichannel spectrophotometer for quick and precise UV/VIS spectral analysis of microliter droplets of DNA. This method allows for the measurement of total and double stranded DNA as well as purity and quality ratios (A260/280 and A260/230).

For whole exome sequencing, a minimum of 1.1 ug of DNA is needed (personal communication, [name]; Department of Laboratory Medicine). Thus for this study purpose, 1.1 ug of DNA will be considered a “sufficient” sample. Whole exome sequencing, using a minimum of 1.1 ug of DNA, sequencing will be performed using sequence type: Exome Sure Select v5 + UTR (71MB) at 50% on target (PE 101 base) on the Version 4 HiSeq instrument.

In order to validate that WES can be performed a subset of 5 samples from each needle will be evaluated by whole exome sequencing using Illumina standard methods. Only samples with at least 5 micrograms of DNA will be evaluated. The WES will be performed in a de-identified manner and will not be used clinically for the care of the patient.

14. All the pathological data collection will done by following guidelines from the Papanicolaou Society of Cytopathology Guidelines^{21, 22}.

8.3 9. STATISTICAL CONSIDERATIONS

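### Section 9.1 powers a paired study with McNemar's test but states only unpaired tests for yes/no outcomes, and no primary variable is named

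*Combined protocol and SAP*

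**What the plan says.** **Test.** Section 9.1 opens by describing a paired sample study. Continuous variables get a paired t-test. Categorical variables are to be "reported as frequencies with percentages and compared using chi-square test" or Fisher's exact test, at a two-sided 0.05 level. The synopsis repeats this rule. McNemar's test appears only in the sample-size paragraph. There it gives 80% power or more with 50 patients to detect "a difference in adequacy proportions between FNA and FNB" of at least 25 points if no more than 38% of patients are discordant, or at least 20 points if no more than 25% are.

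**Endpoint.** Section 2.1 compares the needles "for whole exome sequencing and genomic profiling in tissue sampling of pancreatic solid tumors" and gives no variable, threshold or unit of analysis. The synopsis lists five aims, none marked primary. The first is "Per needle adequacy for un-amplified whole exome sequencing". Section 2.2 places "sufficient DNA to complete un-amplified whole exome sequencing" inside its first secondary objective. Section 8.2 item 13 supplies the cut-off: "Thus for this study purpose, 1.1 ug of DNA will be considered a" sufficient sample.

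**Planning data.** The sample-size paragraph rests on five patients: "using the Foundation Medicine adequacy criteria, 2 (40%) had an adequate sample of DNA with FNA", against all five with FNB. Section 2.2 lists that outcome as another secondary objective: "To compare the yield of tissue sufficient for targeted (Foundation Medicine Assay) genomic profiling of pancreas tumors". The documents give no threshold for it.

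**The concern.** Each patient is sampled with both needles, so the two yes/no results come from the same lesion. A chi-square or Fisher test on the needle totals treats them as two separate groups of 50. When the two results are positively correlated, such a test overstates the variance of the difference and loses power. An analyst who follows Section 9.1 literally would then not run the test on which the sample size was justified.

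The missing primary variable adds to this. WES sufficiency and Foundation Medicine adequacy can both be read as the main outcome, and the two could give different answers. If neither is fixed beforehand, the emphasis can be chosen once the results are known, and it is unclear which result the power statement supports.

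**Working it through.** **Inputs, all from Section 9.1.** 50 pairs; two-sided 0.05. Cell percentages at the limits of the three examples, in the order both adequate / FNB only / FNA only / neither:
- A: 58.5 / 31.5 / 6.5 / 3.5 (FNB 90%, FNA 65%)
- B: 48.5 / 31.5 / 6.5 / 13.5 (80%, 55%)
- C: 68 / 22 / 2 / 8 (90%, 70%)

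**Step 1: reproduce the stated power.** Let b and c be the two discordant proportions. The number of discordant pairs m is binomial (50, b + c). Given m, the number favouring FNB is binomial (m, b/(b + c)). Power is the total probability of outcomes where the test rejects. The exact version rejects when the two-sided binomial p is at most 0.05, the uncorrected version when (difference in counts)²/m is at least 3.84.
- 25 points, 38% discordant (b = 0.315, c = 0.065): exact 81.2%, uncorrected 87.0%.
- 20 points, 25% discordant (b = 0.225, c = 0.025): exact 80.8%, uncorrected 87.2%.

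A normal approximation agrees for the first case: z = (0.25 × √50 − 1.96 × √0.38) / √(0.38 − 0.0625) = (1.768 − 1.208) / 0.563 = 0.99, or 84.0%. The 80% claim is sound for McNemar's test.

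**Step 2: apply the written rule to the plan's own examples.** All four-cell outcomes for 50 pairs were enumerated, and each was tested as two unpaired groups of 50 (chi-square without continuity correction).

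| Test | A | B | C |
|---|---|---|---|
| McNemar, exact | 81.2% | 81.2% | 83.5% |
| McNemar, uncorrected | 87.0% | 87.0% | 89.5% |
| Fisher | 82.0% | 73.1% | 66.9% |
| Chi-square | 87.7% | 80.2% | 78.3% |

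**Step 3: why the examples differ.** Per patient, the variance of the paired difference is (b + c) − (b − c)². The unpaired calculation uses the sum of p(1 − p) over the two needles.
- A: paired 0.38 − 0.0625 = 0.3175; unpaired 0.09 + 0.2275 = 0.3175. These are equal, because A at its limit has no correlation between needles.
- B: paired 0.3175; unpaired 0.16 + 0.2475 = 0.4075.
- C: paired 0.24 − 0.04 = 0.20; unpaired 0.09 + 0.21 = 0.30.

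So pairing gains nothing in A. In B and C the unpaired tests discard the correlation that the examples build in.

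**Step 4: the endpoint, place by place.**

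| Outcome | Synopsis aims | Section 2.1 | Section 2.2 | Threshold | Planning rates |
|---|---|---|---|---|---|
| WES sufficiency | first of five, unranked | WES named, no variable | secondary | 1.1 ug (8.2 item 13) | none |
| Foundation Medicine adequacy | not listed by name | genomic profiling named, no variable | secondary | none given | 2/5 and 5/5 (9.1) |

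No place in the documents settles which is primary. The unit is also open: Section 8.2 item 6 collects research material in a second and third set of passes, and the documents do not say whether these are counted singly or pooled for each needle.

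**The case against.** **The rule may be only descriptive.** The chi-square/Fisher sentence sits under descriptive analyses, and the same section calls the study paired, uses a paired t-test and powers by McNemar. That McNemar was intended is a fair reading. But the text goes straight on to a significance threshold, gives no other rule for categorical outcomes, and never names McNemar as an analysis. With Fisher as its alternative, chi-square is hard to read as McNemar's chi-square.

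**The effect is modest.** The lowest figures need Fisher. The smallest expected counts are about 11, 16 and 10 in A, B and C (50 × 22.5%, 32.5% and 20%), so by common convention, which the plan does not state, chi-square would be used. Only C then falls below 80%, by 1.7 points. With no true difference and the same concordant cells, simulated rejection rates for chi-square are 6.1/3.5/2.5%, so false positives are not the main worry. This stands as a limit on the size of the problem.

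**The powered outcome is not wholly unspecified.** A reader might infer that the 80% belongs to no endpoint at all. Section 9.1 runs continuously from Foundation Medicine DNA adequacy in five patients to the expected difference and then to the power, so Foundation-type adequacy is its natural subject. What remains is that this outcome is listed as secondary and has no threshold.

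**Other stronger readings.** A reader might infer that 1.1 ug must be primary. Section 2.1 names both WES and genomic profiling, so the documents do not settle it. A reader might also infer a shortfall at higher discordance, or with the five preliminary patients removed from the 50. Section 9.1 states its discordance limits openly, and nothing says that the five are among the 50.

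**Conclusion.** The concern holds in two parts. First, the stated analysis rule for categorical outcomes does not match the paired design or the test used for the power. Within the plan's own examples, power falls below 80% in two of three with Fisher (73.1%, 66.9%) and in one of three with chi-square (78.3%). Second, no primary variable is named: WES sufficiency is both the first aim and part of a secondary objective, while the planning data belong to a different secondary objective.

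The figures rest on 50 complete pairs, two-sided 0.05 and the examples at their stated limits. They do not show that the sample size is wrong: under McNemar's test 50 patients and the 80% statement stand. If 1.1 ug becomes primary, the documents give no adequacy or discordance rates for it, so 80% is an assumption for that endpoint and the direction of any error is unknown. The harm from an open choice of endpoint is not quantified here.

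**What to change.** 1. In Section 9.1 and the synopsis, replace chi-square/Fisher by McNemar's test for paired yes/no outcomes, and state whether it is exact or uncorrected.
2. In Sections 2.1, 2.2 and 9.1, the sponsor should name one primary yes/no variable per patient and needle, either 1.1 ug WES sufficiency or Foundation Medicine adequacy. State its threshold and which research passes count, make the other secondary, and bring the objective lists into line.
3. If 1.1 ug is chosen, say in Section 9.1 that the difference and discordance are assumptions for that endpoint.

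Separately, Section 6.3 plans no interim analysis, while Section 9.1 says that the sample size was calculated after one. These should be reconciled, but the point above does not depend on it.

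The cost is wording only. No patients, procedures or assays are added, and 50 patients with 80% power stand under McNemar's test.
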